3.2 Selection of Study Population

This is a phase I/IIa study in adult subjects with relapsed or refractory MM as monotherapy and in combination with standard therapy. Key inclusion criteria identified in the protocol are

1. Male or female subjects ≥ 18 years of age
2. Presence of serum M-protein ≥ 0.5 g per 100 mL (≥ 5 g/L) and/or urine M-protein ≥ 200 mg per 24-hour period
3. Life expectancy of > 3 months
4. Karnofsky performance status $\geq 60\%$
5. Absolute neutrophil count ≥ 1.0 (1,000/mm³)
6. Total bilirubin $\leq 2 \times$ the upper limit of normal (ULN)
7. Alanine transaminase and aspartate aminotransferase $\leq 2.5 \times$ ULN
8. Hemoglobin ≥ 8 g/dL

Additional key inclusion criteria are defined differently for monotherapy and different combination therapies:

Additional Key Inclusion Criteria for Treatment With MOR03087 With/Without Dexamethasone

1. Documented diagnosis of MM; specifically, relapsed or refractory MM defined as:
 - Failure of at least 2 previous therapies; previous therapies must include an immunomodulatory agent and a proteasome inhibitor (either together or as part of different therapies)
 - All subjects must have documented progression during or after their last prior therapy for MM
2. Creatinine clearance ≥ 30 mL/min (calculated using the Cockcroft-Gault equation)
3. Platelets:
 - $\geq 80 \times 10^9/L$, without previous transfusion within the last 4 weeks before first study drug administration

- $\geq 50 \times 10^9/L$ (for dose levels ≥ 4 mg/kg with or without DEX). Subjects are not allowed to have received platelet transfusion within the last 4 weeks before study drug administration.

Additional Key Inclusion Criteria for the Treatment With MOR03087, Dexamethasone and Lenalidomide

1. Documented diagnosis of MM; specifically, relapsed or refractory MM defined as:
 - Received at least 1 previous therapy
 - All subjects must have documented progression during or after their last prior therapy for MM
2. Creatinine clearance ≥ 50 mL/min (calculated using the Cockcroft-Gault equation)
3. Platelets:
 - $\geq 75 \times 10^9/L$ for subjects in whom $< 50\%$ of bone marrow nucleated cells are plasma cells
 - $\geq 30 \times 10^9/L$ for subjects in whom $\geq 50\%$ of bone marrow nucleated cells are plasma cells.

Additional Key Inclusion Criteria for the Treatment With MOR03087, Dexamethasone and Pomalidomide

1. Documented diagnosis of MM; specifically, relapsed and refractory MM defined as:
 - Received at least 2 previous therapies including LEN and a proteasome inhibitor
 - All subjects must have documented progression during or within 60 days after their last prior therapy for MM
2. Creatinine clearance ≥ 45 mL/min (calculated using the Cockcroft-Gault equation)
3. Platelets:
 - $\geq 75 \times 10^9/L$ for subjects in whom $< 50\%$ of bone marrow nucleated cells are plasma cells
 - $\geq 30 \times 10^9/L$ for subjects in whom $\geq 50\%$ of bone marrow nucleated cells are plasma cells

3.3 Method of Treatment Assignment and Randomization

The study is not randomized. Subjects are allocated to open cohorts only. The allocation is performed centrally by the project management. In case more than 1 cohort is open in parallel subjects who meet the inclusion-/exclusion criteria for more than 1 cohort are allocated to 1 of the open cohorts based on a specific cohort assignment plan. The project management department is the owner of the cohort assignment plan and the latest version is Version 6, 30-JUN-2016.

3.4 Treatment Masking (Blinding)

This is an open-label study. No personnel involved in the study will remain blinded.

4. ANALYSIS AND REPORTING

4.1 DMC Analysis

An independent DMC will review the safety data at several timepoints during the study. Details of the safety data output provided for the DMC by Premier Research Biostatistics are described in a separate Statistical Interim Safety Analysis Plan, Final Version 4.0, dated 26-MAY-2015.

4.2 Final Analysis

The analyses identified in the protocol and in this SAP will be performed after all subjects enrolled have reached the Cycle 3 Day 1 visit or end of study assessments (whichever comes first) and all relevant study data have been processed, all relevant data has been frozen and this SAP has been approved. A cut-off date will be determined for the analysis (which will be after all subjects enrolled have reached Cycle 3 Day 1 or end of study assessments) and all data available up to the cut-off date will be included into the analysis. The final analysis is also referred to as “primary completion analysis”.

4.3 Follow-up Analyses

After the final analysis, additional supplemental analyses of long-term efficacy and safety follow-up will be performed. For this analysis, it is planned to re-run all analyses described in this SAP.

Key statistics and study results will be made available to MorphoSys AG following database lock and prior to completion of the final CSR.

Any, post-hoc, exploratory analyses completed to support planned study analyses, which were not identified in this SAP, will be documented and reported in appendices to the CSR. Any results from these unplanned analyses (post-hoc) will also be clearly identified in the text of the CSR.

5. SAMPLE SIZE DETERMINATION

A 3 + 3 design is used for the dose-escalation part of the study with confirmation cohorts of 6 subjects. At least 9 subjects will be analyzed in the recommended dose groups of each part: 6 subjects from the confirmation cohort and at least 3 subjects from the dose-escalation cohort who receive the same dose and regimen and combination treatment (if applicable).

6. ANALYSIS POPULATIONS

The following analysis populations are planned for this study:

Total Population (All Subjects)

The Total Population will consist of all subjects including screening failures.

Safety Population

The Safety Population will consist of all enrolled subjects who received any of the IMP at least once.

DLT Evaluable Population

The DLT Evaluable Population will consist of all enrolled subjects who have received at least 1 cycle of MOR03087 (at least 4 doses for q1w or 2 doses for the q2w dosing schedule) (monotherapy or combination therapy) and if applicable per cohort, at least 16 doses of LEN or POM without dose modifications and who have minimum safety evaluations, including the first

cycle and AEs reported from Day 1 after the start of the first infusion until Day 1 of the second cycle (before start of infusion).

- Subjects who withdraw before having received the minimum number of infusions/doses and safety evaluations due to DLT will be included in the DLT evaluable population.
- Subjects who discontinue study treatment or require a dose modification for LEN or POM for reasons unrelated to a DLT within the first cycle will be excluded from the DLT evaluable population.

Efficacy Evaluable Population

The Efficacy Evaluable Population will consist of all subjects who take at least 1 dose of IMP and who have at least one investigator response assessment (including potential unscheduled response assessment/ visits) after baseline. Only a post-baseline lab value without an Investigator response assessment does not qualify for inclusion.

Pharmacokinetic Population

The Pharmacokinetic Population will consist of all subjects who have sufficient pharmacokinetic data to characterize the time course of MOR03087 or LEN or POM in serum or plasma for the first IMP administration at a minimum.

7. GENERAL ISSUES FOR STATISTICAL ANALYSIS

7.1 General Statistical Methodology

A table for disposition of all subjects (see section 8.1) will be produced for all subjects who provide informed consent, including screening failures. The Safety Population will be used for safety analysis and to analyze immunogenicity and the pharmacodynamic endpoints. The DLT Evaluable Population will be used to determine the maximum tolerated dose. Summaries for the analysis of tumor response will be provided for the Efficacy Evaluable Population and the Safety Population. Pharmacokinetic data evaluation will be not part of this SAP but described in a separate Pharmacokinetic Analysis Plan.

Each safety listing will contain a flag indicating which subjects are DLT-evaluable and which subjects are not DLT-evaluable after the subject number. All listings will be sorted by cohort (if data from more than 1 cohort is presented).

In the tables all available data of subjects including all cycles will be presented unless otherwise specified. For the AE tables presenting DLT, TEAEs by grading and SAEs, additional tables will be produced including data of the first cycle only.

Tabulations of summary statistics, graphical presentations, and statistical analyses will be performed using SAS software, Version 9.4 or later.

Continuous, quantitative variable summaries will include the number of subjects (N) (with non-missing values), mean, standard deviation, median, minimum, maximum, and first and third quartiles. First and third quartile will not be shown in by-cohort-tables (tables of type 1, see section 7.2).

Some of the descriptive summaries (as specified in the subsequent sections) will additionally include the 95%-confidence interval for the mean (absolute) change from baseline. The

confidence interval will be calculated based on the quantiles of the t-distribution assuming normal distribution of the data. Moreover, some of the descriptive summaries (as specified in subsequent sections) will include the 95%-confidence interval for the median (absolute or percentage) change from baseline. The 95%-confidence interval for the median will be calculated without any assumption on the distribution of the data (nonparametric confidence interval). [REDACTED]

Categorical, qualitative variable summaries will include the frequency and percentage of subjects who are in a particular category. Unless otherwise stated the calculation of proportions will be based on the number of subjects of the analysis set of interest. Therefore counts of missing observations will be included in the denominator and presented as a separate category. [REDACTED]

The last pre administration observation will be used as the baseline value for calculating post administration changes from baseline. Thus baseline will be Cycle 1 Day 1 in case there is a value available (not missing) and screening otherwise.

All data obtained on the electronic case report for (eCRF) and entered into the database will be provided in separate data listings showing individual subject values. The planning and reporting of statistical analyses will be carried out as described in the Premier Research Biostatistics standard operating procedures.

Any subject who withdraws from the study will be analyzed with the data available. Imputation of missing values will not be performed.

7.2 Structure of Tables

Three different types of tables will be produced:

- 1) tables for the total study data by cohort
- 2) tables for the total study data by part
 - bi-weekly (Part A)
 - weekly without dexamethasone (Part B)
 - weekly with dexamethasone (Part C)
 - combination with POM (Part D)
 - combination with LEN (Part E)
- 3) tables for recommended dose data by part
 - weekly with dexamethasone (Part C)
 - combination with POM (Part D)
 - combination with LEN (Part E)

The safety and baseline summary tables will additionally contain a summary of the total number of subjects of the corresponding analysis (sub-) group.

In the tables for recommended dose data, all data from the recommended (or MTD) dose levels will be summarized together, i.e. data from the confirmation cohort will be combined with the data from the cohort of the dose escalation scheme that received the same dose and regimen and combination treatment (if applicable).

Summaries of type 2) and 3) will be referred to as combined presentations or combined data in subsequent sections, in contrast to summaries by dose level.

The 95% confidence intervals will only be presented for these combined presentations and will not be presented by dose level due to the small number of subjects by dose level.

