#### **Pharmacokinetic Population**

The Pharmacokinetic Population will consist of all subjects who have sufficient pharmacokinetic data to characterize the time course of MOR03087 or LEN or POM in serum or plasma for the first IMP administration at a minimum.

The Safety Population will be used for safety analysis and to analyze immunogenicity and the pharmacodynamic endpoints. The DLT Evaluable Population will be used to determine the maximum tolerated dose. Summaries for the analysis of tumor response will be provided for the Efficacy Evaluable Population and the Safety Population. Pharmacokinetic summaries will be presented for the Pharmacokinetic Population.

Tabulations of summary statistics, graphical presentations, and statistical analyses will be performed using SAS[®] software.

Continuous, quantitative variable summaries will include the number of subjects (N) (with nonmissing values), mean, standard deviation, median, minimum, maximum, and first and third quartiles.

Categorical, qualitative variable summaries will include the frequency and percentage of subjects who are in the particular category.

In general, data will be summarized by treatment arm (A-E) and dose level.

Furthermore, there will be specific summaries for the recommended dose groups of each treatment arm. Summaries for recommended dose data will combine data from the confirmation

cohort with the data from the cohort of the dose-escalation scheme that received the same dose and regimen and combination treatment (if applicable).

The last pre-administration observation will be used as the baseline value for calculating post-administration changes from baseline. All data obtained on the eCRF and entered into the database will be provided in separate data listings showing individual subject values. The planning and reporting of statistical analyses will be carried out as described in the CRO's SOPs.

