## **15.10 Significance Level**

Confidence intervals, both individual and simultaneous, will be at the 95% confidence level unless stated otherwise.

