At least 3 subjects meeting all inclusion and none of the exclusion criteria, as determined at the screening visit (see sections 8.1 and 8.2 of the study protocol) will be enrolled into each cohort. Enrolment into a cohort at the next higher dose level will be based on the data generated from the previous dose level and guided by DMC review until

- the maximum planned dose has been reached, or
- the review of the safety data indicates a need to either expand the current dose level cohort to include 6 subjects or stop the dose escalation or the study, or
- the review of Part B dose level 6b and Part C dose level 6c, including available safety information from Part A dose level 8, indicates that only some of the planned weekly MOR03087 monotherapy dose escalation cohorts should be tested.

The DMC safety review will take place after the third subject enrolled into a cohort has undergone minimum safety evaluations (as defined for the “DLT Evaluable Population” in section 6). The safety assessment will take into account AEs reported from Day 1 after the start of the first infusion through Day 29 (Cycle 2 Day 1) before the start of the second cycle. The next cohort will only be started after the positive outcome of the safety assessment.

Subjects who withdraw whilst their safety assessment period is not evaluable will only be replaced during the dose-escalation phase until the applicable cohort consists of a sufficient number of evaluable subjects. However, withdrawals due to DLTs will not be replaced.

Cohort expansion up to 6 subjects will be allowed if a dose limiting toxicity (DLT) (as defined in section 8.5 of the study protocol) is observed in 1 of 3 subjects. If 2 or 3 subjects experience a DLT in cohorts 6b or 6c, the study sponsor may decide to test a lower dose. If 2 or 3 subjects of the 3 subjects in any of the other cohorts experience DLT, then the previous cohort should be expanded to 6 subjects.

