10.1 Dose Limiting Toxicities and Maximum Tolerated Dose

One of the primary endpoints will be to determine the MTD or recommended dose and dosing regimen for MOR03087 with or without DEX and in combination with 2 standard IMiD therapies, Lenalidomide and Pomalidomide. This primary endpoint will be determined in the DLT Evaluable Population and will be based on a 4-week safety assessment period (one 28-day cycle).

Following completion of Parts A-C (dose escalation of MOR03087 alone and in combination with DEX using 2 dosing schedules), the MTD and/or recommended dose will be confirmed in a minimum of 6 subjects. Following completion of Parts D and E (dose escalation of MOR03087

in combination with POM + DEX and in combination with LEN + DEX), the MTD and/or recommended dose in each treatment arm will be confirmed in a minimum of 6 subjects.

The recommended doses for the confirmation cohorts will be determined after review of all available safety data from the corresponding dose escalation portion of the study and based on the recommendation of the DMC. The recommended dose may be the MTD or a dose below the MTD.

The MTD is defined as the dose level below the dose level at which 2 out of 3 subjects or 2 out of 6 subjects experience a DLT, as described in the dose-escalation plan (see section 3.1).

All DLTs will be entered as AEs on the Adverse Event Page and identified by the investigator as DLTs by ticking the corresponding field (dose limiting toxicity yes/no). Moreover, there is an additional field on the AE page (hidden for site entry) which contains the information regarding whether the AE is a DLT according to the decision of the sponsor assessment or DMC as documented in the meeting minutes. The additional DLT field will not need to be filled out in case of unambiguous cases.

Thus, the analysis of DLTs will be described within the subsequent sections covering the analysis of AEs. For DLT analyses, DLTs will be filtered based on the following approach. If the field "DLT as per sponsor assessment or DMC decision" is filled out, this field will be used to determine if AE is a DLT, otherwise the field "Is this Adverse Event a Dose-Limiting Toxicity?", which is filled out by the Investigator, will be used.

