- If the start day and months are missing but the start year is complete, an AE will only be excluded from TEAEs if the start year is before the year of first treatment or if the start year is after the end year of the treatment-emergent period or if the stop date/time is before the start of first treatment.
- If the start date is completely missing, an AE will not be excluded from TEAEs unless the stop date/time is before the start of first treatment.

Time from first treatment to onset of AE [days] will be calculated for complete dates only and will be included in listings.

The TEAE grading will be determined by the investigators according to the NCI-CTC toxicity criteria. If a subject experiences a specific type of adverse event more than once, only the maximum grading will be considered in tables of TEAEs by grading when calculating the incidences (number and percentage of subjects with AE of specific type and grade).

One of the primary endpoints will be to determine the incidence and severity of AEs.

A TEAE summary table will be presented showing the incidence and frequency of all

- Treatment-emergent AEs (TEAEs)
- TEAEs by grading (according to NCI-CTCAE toxicity criteria)
- TEAEs with Grade ≥ 3
- TEAEs with Grade 1 and 2
- TEAEs with Grade 3 and 4
- TEAEs related to MOR03087 / Pomalidomide / Lenalidomide / Dexamethasone
- Serious adverse events (SAEs)
- Serious adverse events (SAEs) related to MOR03087 / Pomalidomide / Lenalidomide / Dexamethasone
- MOR03087-related TEAEs by grading (according to NCI-CTCAE toxicity criteria)
- Pomalidomide-related TEAEs by grading (according to NCI-CTCAE toxicity criteria)
- Lenalidomide-related TEAEs by grading (according to NCI-CTCAE toxicity criteria)
- Dexamethasone-related TEAEs by grading (according to NCI-CTCAE toxicity criteria)
- DLTs
- Infusion reactions
- TEAEs leading to any action on MOR03087 / Pomalidomide / Lenalidomide / Dexamethasone
- TEAEs leading to withdrawal of MOR03087 / Pomalidomide / Lenalidomide / Dexamethasone

- TEAEs that caused the subject to withdraw from the study
- Symptomatic overdoses reported as TEAE

The incidence refers to the number and percentage of subjects with at least 1 TEAE of the specified type and the frequency to the number and percentage of AEs.

Exact 95%-confidence intervals for the incidence rates will be included in the summary tables for the combined data.

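### In the recommended-dose tables the pooled DLT rate is biased low, because the escalation cohort in the pool could be carried forward only with fewer than 2 DLTs; no interval is planned for the confirmation cohort alone

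*SAP*

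**What the plan says.** SAP 7.2 plans three types of table: by cohort (type 1), by part (type 2), and recommended-dose data by part for Parts C, D and E (type 3). In type 3, "data from the confirmation cohort will be combined with the data from the cohort of the dose escalation scheme" that had the same dose, regimen and combination. Protocol 15.1 plans the same: "Summaries for recommended dose data will combine data from the confirmation" cohort and the matching escalation cohort. SAP 5 and Protocol 15.9 put the group at 9 subjects or more, 6 from confirmation and at least 3 from escalation.

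On intervals, SAP 7.2 says: "The 95% confidence intervals will only be presented for these combined presentations and will not be presented by dose level"; its stated reason is the small numbers per dose level. SAP 10.2 adds: "Exact 95%-confidence intervals for the incidence rates will be included in the summary tables for the combined data". DLTs are one row of that summary table, and the DLT summaries are limited to cycle 1. Protocol 15.10 sets the level: intervals "will be at the 95% confidence level unless stated otherwise".

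On selection, SAP 10.1 says: "The MTD is defined as the dose level below the dose level at which 2 out of 3 subjects or 2 out of 6 subjects" have a DLT. SAP 3.1 allows expansion to 6 after 1 DLT in 3. Outside cohorts 6b and 6c, if 2 or 3 of 3 have one, "then the previous cohort should be expanded to 6 subjects". The recommended dose is the MTD or lower, chosen on all the safety data and the DMC's recommendation (SAP 10.1). Neither document mentions that the escalation cohort in the pool was screened on its DLT count.

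**The concern.** The confirmation cohort is an unselected sample at the chosen dose. The escalation cohort is not: under the stated rules it is in the pool only because it had fewer than 2 DLTs, and its size (3 or 6) can depend on that same count. Pooling the two and attaching an exact binomial interval treats all 9 to 12 subjects as one unselected sample of fixed size.

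What is at stake is how the DLT rate at the recommended dose is reported. The error runs in the reassuring direction. A reader of a pooled 1/9 is not told that at least 3 of the 9 were carried forward on condition of a low count. By-part tables also carry intervals but pool every dose level, so the pooled figure is the only interval specific to the recommended dose.

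**Working it through.** **Plan's own figures.** Protocol 15.9 gives the chance of seeing an AE at least once among 9 subjects as 81% at a rate of 17% and 90% at 23%. From 1-(1-p)^9: 1-0.83^9 = 81.3% and 1-0.77^9 = 90.5%. Both reproduce.

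**Model.** Let p be the true DLT probability and q = 1-p. The documents give no value for p, so a range is assumed. Subjects are independent, all are evaluable, and the confirmation cohort is Binomial(6, p).

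Path A, straightforward escalation: the cohort passes with 0/3 (probability q^3) or with 1/3 then 0/3, giving 1/6 (probability 3pq^2 × q^3 = 3pq^5).

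- P(pass) = q^3 + 3pq^5
- w0 = q^3 / P(pass); w1 = 1 - w0
- Mean pooled estimate = w0 × 6p/9 + w1 × (1+6p)/12

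At p = 0.17: q^3 = 0.5718 and 3pq^5 = 0.2009, so P(pass) = 0.7727, w0 = 0.740 and w1 = 0.260. The mean is 0.740 × 0.1133 + 0.260 × 0.1683 = 0.128.

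Path B, six subjects treated and at most 1 DLT, as after back-expansion: P(pass) = q^6 + 6pq^5, and the pooled denominator is 12.

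| Assumed true rate | P(pass), A | Mean pooled, A | Bias, A (points) | Mean pooled, B |
|---|---|---|---|---|
| 5% | 0.973 | 4.2% | -0.8 | 4.5% |
| 10% | 0.906 | 8.0% | -2.0 | 8.3% |
| 17% | 0.773 | 12.8% | -4.2 | 13.1% |
| 20% | 0.709 | 14.7% | -5.3 | 15.0% |
| 30% | 0.494 | 21.0% | -9.0 | 21.0% |

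The confirmation cohort alone has expectation p, so its bias is 0.

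**Interval.** The exact upper limit for 0 events in n is 1 - 0.025^(1/n). For 0/9 this is 33.6%. On path A no possible result has a lower upper limit, so the limit never falls below the truth until p exceeds 33.6%. Just above that, 0/9 misses with probability q^9 / P(pass): at p = 0.337 this is 5.9%, against a nominal 2.5%. By then only about 42% of cohorts would pass.

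On path B the smallest upper limit is that for 0/12, 1 - 0.025^(1/12) = 26.5%, so misses begin earlier. At p = 0.30 the miss probability is q^12 / P(pass) = 0.0138/0.4202 = 3.3%.

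**Detection of DLT-type events, path A.** 1 - w0 × q^6 gives 75.8% at 17% and 85.2% at 23%, against 81.3% and 90.5% for 9 unselected subjects.

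**The case against.** The strongest reply is that nothing turns on this number. The dose is decided by the 3+3 counts, the full safety review and the DMC. Neither document uses the pooled rate or its interval to choose or confirm a dose. That stands: a reader might infer that the bias compromises the MTD or recommended-dose endpoint, and the documents do not support it.

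Three other tempting readings also fail.

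- That the escalation cohort is retained purely for its DLT count. Fewer than 2 DLTs is necessary but not sufficient, since the recommended dose may lie below the MTD and rests on all safety data.
- That the exact interval is generally invalid. On path A it has no upper misses at any rate up to 33.6%; excess misses on path B start above 26.5%.
- That the protocol's 81% is wrong. It is stated for AEs in general and is correct for them. Only DLTs and closely correlated events have the lower figure.

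It can also be said that pooling is pre-specified and openly described, that the SAP gives a reason for withholding intervals by dose level, and that by-cohort tables may show confirmation subjects separately. Pre-specification prevents choosing the pool after the fact but does not remove the bias. The by-cohort tables carry no interval. SAP 7.2 does not say whether they split the confirmation cohort from the matching escalation cohort, and because the planned table list is redacted, a separate column cannot be ruled out.

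**Conclusion.** The concern holds as a reporting point of modest importance. The pooled DLT estimate at the recommended dose is biased low: by under 1 point at an assumed true rate of 5%, about 2 at 10%, and about 5 to 9 at 20-30%. Even the larger shifts are small beside the sampling uncertainty: the exact interval for 1/9 is 0.3-48.2%.

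The conclusion rests on the rules as written (fewer than 2 DLTs to pass, with the 2-of-6 criterion taken from the SAP's MTD definition), on independence between subjects, and on assumed true rates. The two paths give similar bias, so the result does not depend on how the cohort came to have 3 or 6 subjects. It is mainly a point-estimate problem, with the interval affected only at high true rates.

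**What to change.** For Parts C, D and E, where a confirmation cohort exists, add to the recommended-dose tables the cycle 1 DLT incidence with an exact 95% interval for the confirmation cohort alone, beside the pooled figure. State this in SAP 7.2 as an exception to the rule against intervals by dose level. Footnote that the pooled DLT rate is conditional on the escalation cohort having passed the 3+3 rule. Keep every planned pooled table.

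The cost is one column or row and a footnote, with no new data and no change in conduct. The downside is precision: at n=6 the exact interval is 0-45.9% for 0/6 and 0.4-64.1% for 1/6, against 0-33.6% for 0/9 and 0.3-48.2% for 1/9. That width shows how much unselected evidence there is.
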